Disease progression	For patients with: $<5\%$ blasts: $\geq 50\%$ increase in blasts to $>5\%$ blasts $5\%–10\%$ blasts: $\geq 50\%$ increase to $>10\%$ blasts $10\%–20\%$ blasts: $\geq 50\%$ increase to $>20\%$ blasts $20\%–30\%$ blasts: $\geq 50\%$ increase to $>30\%$ blasts Any of the following: $\geq 50\%$ decrement from maximum remission/response in granulocytes or platelets Reduction in Hb by ≥ 2 g/dL Transfusion dependence

* Dysplastic changes should consider the normal range of dysplastic changes (modification).

† Modification to IWG response criteria.

‡ In some circumstances, protocol therapy may require the initiation of further treatment (eg, consolidation, maintenance) before the 4-week period. Such patients can be included in the response category into which they fit at the time the therapy is started. Transient cytopenias during repeated chemotherapy courses should not be considered as interrupting durability of response, as long as they recover to the improved counts of the previous course.

Attachment 5: (Continued): International Working Group (IWG) Response Criteria 2006**Proposed modified International Working Group response criteria for hematologic improvement**

Hematologic Improvement*	Response criteria (responses must last ≥ 8 weeks)†
Erythroid response (pretreatment, < 11 g/dL)	Hb increase by ≥ 1.5 g/dL Relevant reduction of units of RBC transfusions by an absolute number of at least 4 RBC transfusion units/8 weeks compared with the pretreatment transfusion number in the previous 8 weeks. Only RBC transfusions given for a Hb of ≤ 9 g/dL pretreatment will count in the RBC transfusion response evaluation†
Platelet response (pretreatment, $< 100 \times 10^9/L$)	Absolute increase of $\geq 30 \times 10^9/L$ for patients starting with $> 20 \times 10^9/L$ platelets Increase from $< 20 \times 10^9/L$ to $> 20 \times 10^9/L$ and by at least 100%†
Neutrophil response (pretreatment, $< 1 \times 10^9/L$)	At least 100% increase and an absolute increase $> 0.5 \times 10^9/L$ †
Progression or relapse after HI‡	At least 1 of the following: At least 50% decrement from maximum response levels in granulocytes or platelets Reduction in Hb by ≥ 1.5 g/dL Transfusion dependence

* Pretreatment counts averages of at least 2 measurements (not influenced by transfusions) ≥ 1 week apart (modification).

† Modification to IWG response criteria.

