4.2 General Analysis Definitions

4.2.1 Baseline and Phase

Unless specified otherwise, the baseline value is defined as the last non-missing value collected from the local laboratory on or before the first dose of study drug for Part 1 and Part 2. For subjects who have been randomized but not treated with any study drug, the randomization date will be used as the reference date for baseline value calculation. For the purpose of analysis, the term "study drug" refers to imetelstat for Part 1, and imetelstat/placebo for Part 2.

For efficacy analysis that relates with Hb, i.e. HI-E (Hb), pretreatment Hb will be used, which is defined as the average of all the Hb values (from transfusion history, local, and central lab) in the

8 weeks prior to the first dose date, including the value on the first dose date (Part 1 or Part 2) and excluding values that were within 14 days after transfusion (thus considered to be influenced by transfusion) for all treated subjects. If there were no Hb values that met this definition of not being influenced by transfusions, then the baseline value (the last non-missing Hb, or the average if multiple values from the same date, from local or central lab collected on or before the first dose) is used.

For subjects who have been randomized but not treated with any study drug, the last non-missing Hb, or the average if multiple values from the same date, from local or central lab collected on or before the randomization date will be used for pretreatment Hb.

For each part of the study:

Screening Phase: up to 28 days during which subject’s eligibility will be reviewed and approved before Study Day 1.

Treatment Phase: extend from Study Day 1 until the date of the last dose. The Treatment Phase will be subdivided by cycles, based on the nominal treatment cycles as recorded on the CRF. Each cycle is planned to be 28 days.

End of Treatment Phase: between date of last dose of study drug +1 day and the End of Treatment Visit, or the earliest of (the last dose date +30 days, death date, or the last contact date if subject lost to follow-up or withdrew consent) when End of Treatment Visit is not performed. The assessments performed during the ‘End-of Treatment Visit’ will be included in this phase.

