4.9.1.4 Examination of Subgroups

Subgroup analyses will be performed to assess the consistency and robustness of the treatment benefit mainly for the rate of RBC TI and the rate of HI-E. Subgroup analysis may be performed for other selected efficacy and safety endpoints. CMH tests between the two treatment groups within each subgroup will be calculated for Part 2.

Note that the following subgroup variables and the cutoff values are subject to change if warranted to better represent the data.

The uniformity of the treatment effect will be examined for, but may not be limited to the following subgroups:

- Sex (male vs. female)
- Age (≤ 65 vs. > 65 years old; ≤ 75 vs. > 75 years old)
- Time since initial diagnosis (< 2 vs. ≥ 2 years)
- WHO Classification (RS+ vs. RS-)
- Prior RBC transfusion burden (≤ 6 vs. > 6 units RBC; < 8 , 8-12, or > 12 units RBC)
- Transfusion burden per IWG 2018 (HTB vs LTB)
- Baseline bone marrow blasts per central lab ($\leq 5\%$ vs. $> 5\%$)
- IPSS risk group (low risk vs. intermediate-1 risk)
- Number of cytopenia (0-1 vs. 2-3)
- Prior ESA use (yes vs. no)
- Baseline serum EPO levels (≤ 500 vs. > 500 mU/mL)
- ECOG score (0 vs. 1-2)
- IPSS-R Cytogenetic risk groups (very good/good, intermediate, or poor/very poor) [3]
- IPSS-R Prognostic risk groups (very low, low, intermediate, high, or very high) [3]
- Baseline platelets (< 150 vs. $\geq 150 \times 10^9/L$)
- Baseline neutrophils (< 1.5 vs. $\geq 1.5 \times 10^9/L$)

All factors will be based on values recorded on the eCRF as indicated above.

The corresponding rate and associated 2-sided 95% CIs will be summarized and presented on a forest plot for the 2 treatment groups of Part 2 respectively, along with the results of the overall analysis for Part 2.

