4.9.3 Key Secondary Efficacy Variables

4.9.3.1 Variables Definition

24-week RBC TI rate

24-week RBC TI rate is defined as the proportion of subjects without any RBC transfusion during any consecutive 24 weeks (168 days) starting from Study Day 1 until subsequent anti-cancer therapy if any. The starting date of 24-week RBC TI must be between Study Day 1 and the date of last dose of study drug + 30 days or End of Treatment Visit whichever occurs first, or Study Day 31 if randomized but not treated.

Time to 8-week (24-week) RBC TI

Time to 8-week (24-week) RBC TI is defined as the interval from Study Day 1 to the first day of the first 8-week (24-week) RBC TI period.

Duration of RBC TI

Duration of RBC TI is defined as the first day of the longest RBC TI period to the date of the first RBC transfusion after the TI period starts. Subjects who have not had an RBC transfusion ending the TI period at the time of analysis or who withdraw from the study will be censored at the date of the last transfusion evaluation or the day before the first date of subsequent anticancer therapy if given, whichever occurs first.

Rate of hematologic improvement, including HI-E, per modified IWG 2006

The modified IWG 2006 criteria [5] for HI define specific responses of cytopenia in the three hematopoietic lineages: erythroid (HI-E), platelet (HI-P), and neutrophil (HI-N). Rate of hematologic improvement is defined as the proportion of subjects who achieve HI-E, or HI-P, or HI-N.

HI-E is defined as a hemoglobin (Hb) increase of at least 1.5 g/dL above pretreatment and lasts at least 8 weeks or reduction of at least 4 units of RBC transfusion units/8 weeks compared with the prior RBC transfusion burden. A valid 8-week period must start before the date of last dose of study drug + 30 days or End of Treatment Visit whichever occurs first, or Study Day 31 if randomized but not treated, and ends before the first transfusion in posttreatment follow-up or the first day of subsequent anti-cancer therapy whichever occurs first. Pretreatment Hb level is defined as the average of all the Hb values (from transfusion history, local, and central lab) in the 8 weeks prior to first dose date, including the value on first dose date (Part 1 or Part 2) and excluding values that were within 14 days after transfusion (thus considered to be influenced by transfusion) for all

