treated subjects. If there were no Hb values that met this definition of not being influenced by transfusions, then the baseline value (the last non-missing Hb, or the average if multiple values from the same date, from local or central lab collected on or before the first dose) is used. For subjects who have been randomized but not treated with any study drug, the last non-missing Hb, or the average if multiple values from the same date, from local or central lab collected on or before the randomization date will be used for pretreatment Hb.

HI-P is defined as absolute increase in platelet count of $\geq 30 \times 10^9/L$ for subjects starting with $> 20 \times 10^9/L$ platelets or increase from $< 20 \times 10^9/L$ to $> 20 \times 10^9/L$ and by at least 100% lasts at least 8 weeks.

HI-N is defined as at least 100% increase in neutrophil count and an absolute increase $> 0.5 \times 10^9/L$ lasts at least 8 weeks.

Progression or relapse after HI is defined as at least 1 of the following, in the absence of another explanation, per modified IWG 2006: a) at least 50% decrement from maximum response levels in granulocytes or platelets; b) reduction in Hb by ≥ 1.5 g/dL; c) transfusion dependence.

Rate of HI-E per revised IWG 2018

For LTB subjects (who received 3 to 7 RBC units in the 16 weeks prior to study entry):

- Clinically meaningful HI-E response per revised IWG 2018 [4] is defined as 16-week RBC TI, i.e. subjects without any RBC transfusion during any consecutive 16 weeks.

For HTB subjects (who received ≥ 8 RBC units in the 16 weeks prior to study entry):

- Major HI-E response per revised IWG 2018 is defined as 16-week RBC TI.
- Minor HI-E response per revised IWG 2018 is defined as a reduction by at least 50% of RBC units over a 16-week period compared with the 16 weeks prior to Study Entry.

Rate of Complete remission (CR), Partial remission (PR) or Marrow complete remission (mCR)

It is defined as the proportion of subjects who achieve CR, PR or mCR per modified IWG 2006. The analysis will be performed in the ITT analysis set as well as in subjects with bone marrow blasts $> 5\%$ at baseline.

Progression Free Survival (PFS)

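### SAP 4.9.3.1 defines HI-P and HI-N without the pretreatment limits of protocol Attachment 5, so subjects without cytopenia can count as responders

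*SAP*

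**What the plan says.** **Protocol.** Section 9.2.2 lists the rate of hematologic improvement by modified IWG 2006 as a secondary endpoint. Section 9.3 bases efficacy evaluation on those criteria and points to Attachment 5. There the platelet row opens "Platelet response (pretreatment" and sets a limit of below 100 ×10⁹/L. The neutrophil row opens "Neutrophil response (pretreatment" and sets a limit of below 1 ×10⁹/L. A footnote takes pretreatment counts as averages of at least two measurements, at least a week apart and not influenced by transfusion. Attachment 5 is the only place where the protocol defines these two lineage responses.

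**SAP 4.9.3.1.** The endpoint carries the same modified IWG 2006 label, and the introduction says that the criteria "define specific responses of cytopenia in the three hematopoietic lineages". The operational text follows. "HI-P is defined as absolute increase in platelet count of" at least 30 ×10⁹/L for subjects starting above 20 ×10⁹/L, or a rise from below to above 20 ×10⁹/L of at least 100%, lasting at least 8 weeks. "HI-N is defined as at least 100% increase in neutrophil count and an absolute increase" of more than 0.5 ×10⁹/L, lasting at least 8 weeks. Neither definition has an upper pretreatment limit, and no other SAP section supplies one. Overall hematologic improvement is HI-E or HI-P or HI-N.

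**Pretreatment value.** The SAP has an averaging rule for hemoglobin only. For other laboratory values, SAP 4.2.1 says that "the baseline value is defined as the last non-missing value collected from the local laboratory on or before the first dose".

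**The concern.** In Attachment 5 the pretreatment limit belongs to each lineage's criterion: a lineage that was not low cannot improve. The SAP carries over the size and duration of the rise but not the condition on who can be assessed. A programmer coding the SAP text would give every eligible subject a route to response through platelets and through neutrophils. A programmer coding Attachment 5 would close both routes to most subjects.

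The SAP does spell out a baseline restriction elsewhere. For CR, PR and mCR it states: "The analysis will be performed in the ITT analysis set as well as in subjects with bone marrow blasts" above 5% at baseline. HI-P and HI-N have no such statement.

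At stake are the HI-P, HI-N and overall improvement rates. SAP 4.9.3.2 compares the overall rate between arms by the method used for 24-week TI (stratified CMH). The same definitions feed the descriptive Part 1 summary.

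**Working it through.** The documents state no HI-P or HI-N rate, so there is no planned figure to reproduce. The check compares the two rules (counts in ×10⁹/L).

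| Lineage | Rise required (both documents) | Limit, Attachment 5 | Limit, SAP | Entry (protocol 4.1) |
|---|---|---|---|---|
| Platelets | ≥30 if starting >20; or from <20 to >20 and ≥100% | <100 | none | ≥75 |
| Neutrophils | ≥100% and >0.5 | <1 | none | ≥1.5 |

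**1. Who can respond.** If the entry value holds, Attachment 5 leaves platelets from 75 to below 100 for HI-P and nobody for HI-N. With the averaging footnote and one value at 1.5, a two-value mean below 1 needs (1.5 + x)/2 < 1, so x < 0.5. Hence almost nobody is evaluable for HI-N. Under the SAP text everybody is.

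**2. Individual cases, each sustained for 8 weeks.**

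| Change | SAP text | Attachment 5 |
|---|---|---|
| Platelets 80 to 112 | response | response |
| Platelets 150 to 180 | response | no |
| Platelets 250 to 280 | response | no |
| ANC 0.8 to 1.7 | response | response |
| ANC 2.0 to 4.0 | response | no |

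**3. How demanding a rise of 30 is.** Relative rise = 30/start: 40% at 75, 30% at 100, 20% at 150, 12% at 250. The rule is strict inside the Attachment 5 band and loose above it.

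**4. Illustration of chance HI-P.** The documents give no baseline platelet distribution and no within-subject variability, so every input here is assumed: no true change, one baseline value, 12 independent four-weekly values, and response = three consecutive values at least 30 above baseline.

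| Mean platelets | SAP text, CV 10 / 15 / 20% | With the <100 limit |
|---|---|---|
| 90 | 0.2 / 2.8 / 7.9% | 0.2 / 2.8 / 7.9% |
| 150 | 4.4 / 13.5 / 21.0% | 0.1 / 1.3 / 4.7% |
| 250 | 16.3 / 26.4 / 32.7% | 0 / 0 / 0.1% |
| 350 | 24.9 / 33.7 / 38.6% | 0 / 0 / 0% |

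This model does not apply the entry limit to the baseline draw, so the row for 90 is if anything high. A second model applies the entry limit, follows the Table 3 visit schedule over 8 cycles, and assumes CV 10–20% and four-week autocorrelation 0–0.6. Under the SAP text it gives 0–1.4% at a mean of 80, 0.1–7% at 100, 0.8–15% at 125, and 2–36% across 150–300. The answer depends mainly on where baseline counts lie, and the documents do not say.

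**5. Overall rate.** HI-P adds only subjects who are not already HI-E responders. If the two are independent, the addition is HI-P × (1 − HI-E). At the 71% HI-E rate in protocol 1.1.5, 10 points of chance HI-P add 10 × (1 − 0.71) = 2.9 points. The ceiling is the full 10 points. No placebo HI-E rate is given, so the difference between arms cannot be computed.

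**The case against.** **The citation may import the limits.** The SAP names modified IWG 2006, speaks of responses of cytopenia, and serves a protocol that binds the endpoint to Attachment 5. On that reading, counting 250 to 280 contradicts the SAP's own introduction. This shows what was probably intended. It does not settle the programming: the introduction gives no number, and the definitions that follow look complete, down to the starting count of 20.

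**The consequence is modest.** This stands. SAP 4.9.1.3 tests 24-week TI, then HI-E, then PFS and OS. The overall improvement rate is not in that sequence.

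**The limit does not remove chance response.** Also true. Near the cut-off, chance HI-P is the same under both rules (row for 90 above).

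**Stronger readings that the documents do not support:**
- *The SAP expects mostly normal platelet counts, because the subgroup list in 4.9.1.4 splits "Baseline platelets" at 150.* The same list splits neutrophils at 1.5 although entry requires at least 1.5, and it calls its cut-offs subject to change. The split is not evidence of the expected distribution.
- *The omission favours imetelstat.* Protocol 1.1.5.2.1 reports Grade 3 or higher thrombocytopenia in 31 of 57 Part 1 subjects, with most cytopenias resolving in about 4 weeks. If Day 1 platelets stay lower on imetelstat, chance HI-P falls mainly on placebo. If they recover by Day 1, it is similar in both arms and dilutes the comparison.
- *The HI-E gatekeeper has the same fault, because Attachment 5 also sets a hemoglobin limit.* Protocol 9.3.1.2 gives its own adapted HI-E definition without that limit, and the SAP follows it.

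**Conclusion.** The SAP text for HI-P and HI-N departs from the protocol criteria that it cites and should be corrected. That rests on the wording of the two documents and the entry criteria, and needs no assumption. As written, subjects with normal platelets or neutrophils can be responders. Under Attachment 5, roughly only those with platelets from 75 to below 100 ×10⁹/L are evaluable for HI-P, and almost none for HI-N.

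The reach is limited to HI-P, HI-N and the overall improvement rate. The primary endpoint, 24-week TI, HI-E, PFS, OS and control of alpha are unaffected. Neither the size nor the direction of the effect on the overall comparison can be derived from the documents. The simulated rates are illustrations: over assumed mean counts from 80 to 350 they run from about 0 to 39%, and no single value in that range should be quoted as the expected excess.

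**What to change.** Before unblinding, amend SAP 4.9.3.1:

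1. Require pretreatment platelets below 100 ×10⁹/L for HI-P and pretreatment ANC below 1 ×10⁹/L for HI-N, as in Attachment 5.
2. Report HI-P and HI-N rates among subjects evaluable for that lineage, with the evaluable number per arm.
3. In the ITT overall rate, keep all subjects in the denominator but count nobody as a responder through a lineage whose limit is not met.
4. Optionally, to match the Attachment 5 footnote, define pretreatment platelets and ANC as the average of at least two values at least a week apart and not influenced by transfusion, with the SAP 4.2.1 baseline as fallback. In the second model, averaging without the limit lowers chance HI-P by at most 4 points, so the limit does the work.

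The cost is SAP wording and reprogramming, with no protocol change and no new data. Reported improvement rates will be lower, the HI-P evaluable set small and the HI-N set probably empty.

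One related gap remains. Protocol 6.1.1 permits G-CSF and transfusion for cytopenias, and the SAP does not say how on-study counts under such support enter HI-N or HI-P. The same amendment could state this.
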